7.4.2. Dose Adjustment for Rituximab

The dose of rituximab should not be reduced. Administration of rituximab may be interrupted and modified according to the clinical practice of the Investigator's institution (eg, dose splitting or dose banding), and in line with the approved prescribing information including administration, warnings, precautions, contraindications, and adverse reactions, as applicable. In case a dose of rituximab is missed during Cycle 1 because of toxicity, it will not be rescheduled. In case of delay in the start of the next cycle (Cycles 3 through 6) due to toxicity, rituximab administration will be postponed until AE has resolved, at which point the next cycle is started. If rituximab is discontinued due to toxicity, tazemetostat should be continued as per protocol and the subject should continue in the study.

7.5. Continuation of Treatment

Subjects will receive study treatment for 24 cycles across the clinical trial or until disease progression, unacceptable toxicity, or withdrawal of consent. However, if subjects experience disease progression during study treatment, they may be permitted to continue treatment on study

^a Excluding alopecia and nausea, vomiting or diarrhea not receiving adequate treatment

^b An interruption of tazemetostat for more than 14 days due to any toxicity must be discussed with the Medical Monitor before treatment can be resumed

^c Excluding Grade 2 and 3 anemia: subjects are allowed to continue tazemetostat at their current dose level with transfusion per Investigator discretion

^d Excluding Grade 2 neutropenia and thrombocytopenia

^e Use of growth factors (G-CSF, GM-CSF) is permitted as per ASCO or institutional guidelines

f Subjects are allowed to receive platelet transfusion per Investigator discretion

post-progression if they meet the 2014 Lugano Classification (Cheson, 2014; Appendix 3) criteria for disease progression as well as the following criteria:

- absence of symptoms and signs (including worsening of laboratory values, eg, new or worsening hypercalcemia) that indicate unequivocal disease progression
- no decline in ECOG performance status
- absence of tumor growth at critical anatomical sites (eg, leptomeningeal disease) that cannot be managed by protocol-allowed medical interventions

Subjects whose radiographic disease progression is confirmed at a subsequent tumor assessment may be considered for continued study treatment at the discretion of the Investigator if they have evidence of clinical benefit and continue to meet the above criteria. Investigators who note subjects with disease progression that are receiving continued clinical benefit without clinical deterioration must contact the Medical Monitor to discuss the assessment of risk/benefit of maintaining the subject on study.

7.6. Criteria for Study Termination

The Sponsor reserves the right to discontinue the study for medical reasons or for any other reason at any time. If the study is prematurely terminated or suspended, the Sponsor will promptly inform the Investigators/institutions and the regulatory authority(ies) of the termination or suspension and the reason(s) for the termination or suspension. The IRB/IEC will also be informed promptly and provided with the reason(s) for the termination or suspension by the Sponsor or by the Investigator/institution, as specified by the applicable regulatory requirement(s). Study records must be retained as noted in Section 18.

7.7. Schedule of Procedures/Assessments

Schedule of Visits and Procedures for assessments are presented in Table 2.

Potential subjects will undergo a screening assessment within 28 days before the start of the study to evaluate their eligibility for the study. Before any procedures or assessments are performed, the nature of the study, and the potential risks associated with the study will be explained to all subject candidates and written informed consent will be obtained. Once informed consent has been obtained, study procedures and evaluations will be performed.

If Screening is done within 72 hours of Cycle 1 Day 1 (C1D1), local laboratory tests and physical exam do not need to be repeated.

Efforts should be made to conduct study visits on the day scheduled. Whenever possible, subjects should be evaluated at approximately the same time of the day (eg, morning or afternoon) at each visit, and reasonable efforts should be made to conduct all evaluations in the same test order at each visit.

Table 2: Schedule of Visits and Procedures

Procedures/ Assessments ^a	Screen-ing ^b		Cyc	cle 1		Сус	ele 2	Cycle 3	Cycle 4	Cycle 5		Cycles 9, 12, 15, 18, 21, & 24 ^c	FOT		Surviva l Follow up ^f
Cycle Day	Day (-28 to -1)	Day 1 (± 1 Days)	Day 8 (± 1 Days)	Day 15 (± 1 Days)	Day 22 (± 1 Days)	Day 1 (± 3 days)	Day 15 (± 3 days)	Day 1 (± 7 days)	7 Days After	30 Days After Last Dose (+5 Days)	90 Days				
Site visit	X	X	X	X	X	X	X	X	X	X	X	X	X		
Phone call														X	X
Informed consent	X														
Inclusion/exclusion criteria	X	X ^b													
Demographics, medical and surgical history, and prior and current medications	X														
Viral serology/virology ^g	X														
Pregnancy test ^h	X	X^h				X		X	X	X	X	X^h	X	X	
Height	X														
Body weight	X	X	X	X	X	X	X	X	X	X	X	X	X		
Comprehensive physical examination	X												X		
Symptom-directed physical examination		X				X		X	X	X	X	X			

Procedures/ Assessments ^a	Screen-ing ^b		Сус	cle 1		Сус	le 2	Cycle 3	Cycle 4	Cycle 5	Cycle 6	Cycles 9, 12, 15, 18, 21, & 24 ^c	FOTd	Safety Follow- up ^e	Surviva l Follow up ^f
Cycle Day	Day (-28 to -1)	Day 1 (± 1 Days)	Day 8 (± 1 Days)	Day 15 (± 1 Days)	Day 22 (± 1 Days)	Day 1 (± 3 days)	Day 15 (± 3 days)	Day 1 (± 7 days)	Within 7 Days After Last Dose	30 Days After Last Dose (+5 Days)	Every 90 Days (± 30 Days)				
ECOG performance status	X	X				X		X	X	X	X	X	X		
Vital sign measurements ⁱ	X	X	X	X	X	X	X	X	X	X	X	X	X		
Clinical laboratory to	ests ^j	•	•	•			•	•	•	•	•	•	•	•	•
Comprehensive metabolic (chemistry) panel	X ^b	X				X		X	X	X	X	X	X		
LDH	X ^b	X						X				X (Cycle 24 only)	X		
Hematology	X ^b	X	X	X	X	X	X	X	X	X	X	X	X		
Peripheral blood smear ^k	X ^b	X	X	X	X	X	X	X	X	X	X	X	X		
Bone marrow aspirate/biopsy for AESI ^k	spirate/biopsy for Dependent upon peripheral blood smear morphology results														
CT (neck, chest, abdomen, pelvis) ^{l,}	X							X			X	X ^m (Cycles 12, 18, & 24 only)	X ^l		X ^m

														21 000	001 2021
Procedures/ Assessments ^a	Screen-ing ^b		Сус	ele 1		Cyc	ele 2	Cycle 3	Cycle 4	Cycle 5	Cycle 6	Cycles 9, 12, 15, 18, 21, & 24 ^c	FOTd	Safety Follow- up ^e	Surviva l Follow up ^f
Cycle Day	Day (-28 to -1)	Day 1 (± 1 Days)	Day 8 (± 1 Days)	Day 15 (± 1 Days)	Day 22 (± 1 Days)	Day 1 (± 3 days)	Day 15 (± 3 days)	Day 1 (± 3 days)	Day 1 (± 3 days)	Day 1 (± 3 days)	Day 1 (± 3 days)	Day 1 (± 7 days)	Within 7 Days After Last Dose	30 Days After Last Dose (+5 Days)	Every 90 Days (± 30 Days)
¹⁸ FDG-PET ^{1, n}	X							X			X ⁿ	X ⁿ (Cycles 12, 18, & 24 only)	X ^l		X ⁿ
Bone marrow biopsy (with IHC) for disease assessment ^o	Xº	At f	At first notation of possible CR if bone marrow involvement at screening and when clinically indicated ^m												
AE ^p	Collec	llected from time of signing informed consent form to either 30 days after discontinuation of study treatment or until initiation of subsequent anticancer therapy							ent or	X					
Concomitant medications/ procedures	X	Conti	nuous fr	om the fir			rug to eith n of subse				ion of stu	dy treatm	ent or	X	
Tissue for EZH2 mutation testing ^q	X														
Dispense and administer continuous 28-day cycles of tazemetostat, 800 mg BID, PO		Х				X		X	Х	Х	X	X			
Administer rituximab, IV or SC		Xr	Xs	Xs	Xs			Xs	Xs	Xs	Xs				
Survival status and														X	X

Procedures/ Assessments ^a	Screen-ing ^b		Cyc	le 1		Cyc	le 2	Cycle 3	Cycle 4	Cycle 5		Cycles 9, 12, 15, 18, 21, & 24 ^c			Surviva l Follow up ^f
Cycle Day	Day (-28 to -1)	Day 1 (± 1 Days)	Day 8 (± 1 Days)	Day 15 (± 1 Days)	Day 22 (± 1 Days)	Day 1 (± 3 days)	Day 15 (± 3 days)	Day 1 (± 3 days)	Day 1 (± 7 days)	7 Days After	30 Days After Last Dose (+5 Days)	90 Days (+ 30			
subsequent anticancer therapy															

^a All **assessments** must be performed pre-dose and within the visit specified windows, unless otherwise described. Additional unscheduled safety and efficacy assessments may be performed at any time as clinically indicated to determine the relevance of specific findings and/or the duration of events.

^c Subjects may continue treatment with tazemetostat beyond 24 cycles until disease progression, unacceptable toxicity or withdrawal of consent. Procedures/Assessments required every 3 months (ie, C27D1, C30D1, etc), unless otherwise described, until EOT.

- ^e **Safety follow-up** will be performed 30 days (+5 days) after the last dose of study drug. AE and concomitant medication data must be collected for 30 days after the final dose of study drug, or until the start of a new anticancer therapy, whichever occurs first.
- f Survival follow-up will be conducted approximately every 90 days on all subjects, unless consent is withdrawn. Information on all anticancer therapies will be collected (the Sponsor may choose to stop the collection of therapies after the first anticancer treatment following tazemetostat). This may be done by telephone contact. Once the study has achieved the number of events necessary for the final analysis, subjects may no longer be contacted for this information.
- ^g Viral serology/virology testing: If infection status is unknown, testing should include viral serologies for HBV (Appendix 7) and HCV (Appendix 8), and virology testing for HBV and HCV (as indicated), and HIV as per institutional standard. Additional HBV-DNA testing by PCR may be required if subject is HBsAg negative, anti-HBs positive and/or anti-HBc positive. Hepatitis C virus testing by HCV antibody and if positive (reactive), further HCV-RNA testing by PCR must be performed.
- h **Pregnancy testing:** Serum pregnancy test (β-hCG) must be performed at Screening and within 24 hours prior to the first dose of study drug on Cycle 1 Day 1 for all FCBP. A urine or serum pregnancy test will be performed pre-dose on Day 1 of each cycle beginning with Cycle 2 and at the End-of-Treatment visit. Pregnancy tests will have a minimum sensitivity of 25 mIU/mL. Any positive urine pregnancy test must be confirmed by a serum test.
- ¹ Vital signs include blood pressure, heart rate, and body temperature. Blood pressure and heart rate will be collected after the subject has been sitting for 5 minutes.
- Clinical laboratory tests will be performed by Investigators per standard of care. Unscheduled visits may be performed at any time for additional clinical laboratory assessments (samples collected at clinic visit or site's local laboratory) as clinically indicated. See Table 7 for additional information.
- k At screening and during the study, a **peripheral blood smear** will be performed manually or automated along with routine hematology testing and assessed for abnormal morphology. If results are abnormal and suggestive of MDS/AML or MPN, the subject will undergo a bone marrow aspirate/biopsy procedure. The

b Screening period extends from Day -28 to Day -1. Screening laboratory assessments may be used as Day 1 assessments if performed within 72 hours of the first dose of study treatment; however, subjects must continue to meet eligibility criteria prior to first dose of tazemetostat on Cycle 1 Day 1. All site visits in Cycle 1 have a ± 1-day window. All site visits in Cycles 2, 3, 4, 5, and 6 have a ± 3-day window. All site visits starting in Cycle 9 have a ± 7-day window.

^d The **end-of-treatment assessments** must occur within 7 days after treatment discontinuation (eg, at the visit at which the decision to discontinue treatment occurs).

bone marrow aspirate/biopsy sample will then be analyzed by cytogenetic testing at the local laboratory to closely monitor subjects for abnormalities known to be associated with MDS (eg, del 5q, chr 7, abn) and MPN (eg, JAK2 V617F). Additional local laboratory testing of genetic aberrations associated with MDS/AML or MPN can be conducted using targeted next generation sequencing (NGS) of known disease genes, as necessary. If local testing is unavailable or if results are inconclusive/indeterminate, the site will be required to ship samples for central laboratory testing. If the cytogenetic testing and, if conducted, DNA sequencing by NGS results are abnormal and associated with myeloid malignancies, tazemetostat will be discontinued.

- Tumor response assessments by disease-appropriate standard criteria (2014 Lugano Classification [Appendix 3]) using ¹⁸FDG-PET and CT, or combined as PET-CT, of known sites or newly suspected sites of disease (neck, chest, abdomen, and pelvis required at all time points). MRI instead of CT if clinically indicated. Additional imaging of brain or bone by MRI or CT if clinically indicated at screening and during the study for CNS signs/symptoms or bone marrow involvement. Radiologic tumor assessments will be performed at screening between day -28 and day -1 and at specified time points (±7 days) during study treatment beginning from start of treatment (C1D1), irrespective of treatment delays, until loss of clinical benefit or disease progression (i.e., C3D1, C6D1, C12D1, C18D1, C24D1, etc). CT imaging (as PET-CT or CT alone) must include diagnostic quality CT scan AND should preferably be contrast enhanced; FDG-avid disease should report PET-CT based response, non FDG-avid disease should report CT based response. Tumor assessment at EOT required if no disease progression previously documented. Subjects who discontinue study treatment for any reason other than disease progression will continue to undergo tumor response assessments at timepoints (±7 days) as scheduled until disease progression. A standard-of-care clinical examination for lymphoma, including assessment of B symptoms, will be performed at screening and with tumor assessments (See Section 11).
- ^m CT of neck, chest, abdomen, and pelvis required at screening then during study treatment (±7 days) at C3D1, C6D1, C12D1, C18D1, and C24D1, as well as EOT. If no disease progression previously documented and subject continues treatment with tazemetostat beyond 24 cycles, CT will be required every 6 months (±7 days) at C30D1, C36D1, etc. During Survival Follow-up, CT performed every 6 months (±30 days) for 2 years then every 12 months (±30 days) thereafter, or until disease progression (See Section 11).
- ⁿ ¹⁸FDG-PET required at screening then during study treatment at C3D1 (±7 days). ¹⁸FDG-PET also required at the first notation of possible CR and thereafter (C6D1, C12D1, C18D1, and C24D1) may be performed as clinically indicated, except required at EOT. If no disease progression previously documented and subject continues treatment with tazemetostat beyond 24 cycles, ¹⁸FDG-PET as clinically indicated every 6 months (±7 days) at C30D1, C36D1, etc. During Survival Follow-up, ¹⁸FDG-PET may be performed as clinically indicated, in addition to CT, every 6 months (±30 days) for 2 years then every 12 months (±30 days) thereafter, or until disease progression (See Section 11).
- ^o For purposes of disease assessment, a **bone marrow biopsy (including IHC)** will be performed during screening for those subjects with a history of lymphoma involvement of the bone marrow if a bone marrow biopsy with IHC has not been performed within 42 days of C1D1. A written approval from the Medical Monitor is needed if the bone marrow biopsy with IHC has been performed outside of this time window. At the first notation of possible CR and when clinically indicated, a repeat bone marrow biopsy should be performed if lymphoma involvement of the bone marrow was reported at screening. If bone marrow biopsy is not performed at CR, ¹⁸FDG-PET will be used to confirm CR (Perry, 2016; Rutherford, 2017).
- ^p **AEs** will be collected from the time the subject signs the informed consent form until the end of the safety reporting period (or until screen failure). The safety reporting period ends at the time of the safety follow-up visit, 30 days after the last dose of study drug, or initiation of an investigational agent or anticancer therapy, whichever occurs first.
- ^q All enrolled subjects will be required to submit tissue for assessment of EZH2 mutation status. If archival formalin fixed paraffin embedded (FFPE) tumor tissue is not available or will be more than 15 months old at C1D1, subjects will provide a fresh biopsy.
- ^r Dose to be administered: rituximab 375 mg/m² IV. Note: On days when both drugs are administered, tazemetostat should be taken prior to the dosing of rituximab.
- S Dose to be administered: rituximab 375 mg/m² IV **or** rituximab hyaluronidase SC as 1,400 mg rituximab and 23,400 units hyaluronidase per 11.7 ml total volume (120 mg/2,000 units per mL). Note: On days when both drugs are administered, tazemetostat should be taken prior to the dosing of rituximab.

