11.4. Survival Follow-up

Survival follow-up will be conducted approximately every 90 days on all subjects, unless subject withdraws consent. Information on all anticancer therapies will be collected (the Sponsor may choose to stop the collection of therapies after the first anticancer treatment following tazemetostat). This may be done by telephone contact. Once the study has achieved the number of events necessary for the final analysis, subjects may no longer be contacted for this information.

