12.2. Adverse Events

12.2.1. Definition of Adverse Events

12.2.1.1. Adverse Events

An AE is any untoward medical occurrence in a subject or clinical investigation subject administered an investigational product. An AE does not necessarily have a causal relationship with the investigational product. An AE can therefore be any unfavorable and unintended sign (including an abnormal laboratory finding), symptom, or disease temporally associated with the use of an investigational product, whether or not related to the investigational product.

Laboratory values that are deemed not clinically significant or related to underlying disease do not need to be captured as AEs. Laboratory values that warrant treatment change or result and an SAE do need to be captured as applicable.

Events that do not meet the definition of an AE include:

- Medical or surgical procedure (eg, endoscopy, appendectomy); the condition that leads to the procedure is an AE
- Situations where an untoward medical occurrence did not occur (social and/or convenience admission to a hospital)
- Anticipated day-to-day fluctuations of pre-existing disease(s) or condition(s) present or detected at the start of the study that do not worsen

All AEs will be collected from time of signing informed consent to 30 days after the final dose of study drug, or until the start of subsequent anticancer therapy, whichever happens first. If subject is unable to return to the clinic for assessment of AEs this may be done by [contact]. Serious Adverse Events

A SAE is any adverse event (untoward medical occurrence) that at any dose:

- Results in death
- Is life-threatening (ie, the subject was at immediate risk of death from the AE as it occurred; this does not include an event that, had it occurred in a more severe form or was allowed to continue, might have caused death)
- Requires inpatient hospitalization or prolongation of existing hospitalization
- Results in persistent or significant disability/incapacity, or
- Is a congenital anomaly/birth defect (in the child of a subject who was exposed to the study drug)

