12.4. Reporting Adverse Events

All AEs will be recorded from the signing of consent form until 30 days following the last study drug administration. All SAEs must be reported to Sponsor within one business day of the first awareness of the event. The Investigator must complete, sign and date the SAE pages, verify the accuracy of the information recorded on the SAE pages with the corresponding source documents, and send a copy to Sponsor. Any SAEs considered possibly or probably related to the investigational product and discovered by the Investigator at any time after the study should also be reported.

A copy of all additional follow-up information, if required or available, should be sent to Sponsor within one business day of receipt and this should be completed on a follow-up SAE form, placed with the original SAE information, kept with the appropriate section of the eCRF and Investigator Study File.

Epizyme is responsible for notifying the relevant regulatory authorities of certain events. It is the Principal Investigator's responsibility to notify the IRB or IEC of all SAEs that occur at his or her site in accordance with IRB/ IEC guidelines. Investigators will also be notified of all unexpected, serious, drug-related events (7/15 Day Safety Reports) that occur during the clinical trial or at other trials using the same study drug. Each site is responsible for notifying its IRB or IEC of these additional SAEs.

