12.4.1. Reporting of Adverse Events of Special Interest

All potential and identified AESIs, irrespective of their relationship to study drug, must be reported as soon as possible, but no later than 24 hours from when the Investigator becomes aware of the event.

All potential and identified AESIs must be discussed with the Medical Monitor.

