14.7. Criteria for Early Stopping Due to Unacceptable Rates of Adverse Events

Criteria will be in place for halting enrollment and treatment due to safety findings:

- Any fatality that is at least possibly related to treatment calls for immediately stopping accrual and treatment. If attribution is in doubt, the study should be halted until attribution is definitively determined and a decision is made by the study team.
- Two or more observations of a secondary myelodysplastic syndrome or AML or secondary malignancy attributed to tazemetostat will result in stopping accrual and treatment. (Note: observations may not occur during the study period and may occur later, after it is too late to stop accrual.)
- Continuous monitoring with Pocock-like boundaries using the method of Ivanova (Ivanova, 2005) will be utilized for other categories of adverse events, with following rates applied to the continuous stopping rules:
- Combined rate of reportable SAE or SUSAR: 10%
 - Any single category of grade > 3 AE: 50%
 - Grade >3 non-hematologic AE overall: 30%

A table of stopping boundaries for these criteria are provided in Appendix 5. These criteria are independent of the futility analysis for efficacy and will be applied to all subjects that receive any treatment with tazemetostat, regardless of mutation status. See Appendix 2 for details. The stopping rules assume a full accrual of 54 subjects in order to retain statistical properties.

However, if the study stops early due to futility, any bias introduced in the stopping rules due to a change in total accrual should no longer be a concern.

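### Once the safety window closes, no scheduled contact asks about second malignancies, so late cases depend on spontaneous reporting, and the protocol's reporting windows disagree

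*Protocol*

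**What the plan says.** **When collection ends.** Protocol Table 2, footnote p: "The safety reporting period ends at the time of the safety follow-up visit, 30 days after the last dose of study drug", continuing "or initiation of an investigational agent or anticancer therapy, whichever occurs first". Footnote e and Section 12.2.1.1 agree; the latter closes AE collection at 30 days "or until the start of subsequent anticancer therapy, whichever happens first". Section 12.4 gives a different limit: "All AEs will be recorded from the signing of consent form until 30 days following the last study drug administration", with no cut-off at new therapy. Section 12.2.3 likewise requires all SAEs, related or not, up to 30 days after treatment ends, again without that cut-off.

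**What may be reported later.** Section 12.4 extends reporting to "Any SAEs considered possibly or probably related to the investigational product and discovered by the Investigator at any time after the study". Section 12.4.1 says: "All potential and identified AESIs, irrespective of their relationship to study drug, must be reported as soon as possible", within 24 hours of awareness, and gives no end date. Section 12.2.2 sends AESIs through the Section 12.4 procedure.

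**What follow-up collects.** The Survival Follow-up column of Table 2 carries survival status, subsequent anticancer therapy and imaging. Section 11.4 places the contacts about every 90 days and adds: "Once the study has achieved the number of events necessary for the final analysis, subjects may no longer be contacted for this information". CT continues until progression (Table 2, footnote m; Section 11.1). Blood smears end at the End-of-Treatment visit.

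**What uses the counts.** Section 14.7 stops accrual and treatment at two or more secondary MDS, AML or other secondary malignancies attributed to tazemetostat, and remarks that "observations may not occur during the study period and may occur later, after it is too late to stop accrual". Section 12.5 charges the External Safety Committee with evaluating secondary-malignancy signals.

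**The concern.** Section 14.7 names a class of event, says it may appear late, and attaches a two-event rule to it. The visit schedule has no step designed to find that event once the safety window has closed. A second malignancy must be found before anyone can judge whether tazemetostat caused it. Subjects who stop early and move to another therapy have the shortest window, and they may do so while others are still being enrolled or dosed.

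At stake is how complete the information is on which the two-event rule and the External Safety Committee rely. There is also a practical matter for sites: as written, two investigators with the same late case could follow different sections and reach different answers about whether to report it.

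**Working it through.** **1. The plan's own detection figure.** Section 14.6 says that an AE with a true rate of 5% has a 93% chance of being seen at least once in 54 subjects. Check: 1 − 0.95^54 = 0.937. It reproduces. The formula counts every event as recorded.

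**2. The windows side by side.**

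| Place | Events | End of window |
|---|---|---|
| Table 2, footnotes e and p; Section 12.2.1.1 | AEs | 30 days or new therapy, whichever is first |
| Section 12.2.3 | SAEs, any relationship | 30 days |
| Section 12.4 | AEs | 30 days |
| Section 12.4 | Related SAEs that the investigator discovers | None |
| Section 12.4.1 | AESIs, any relationship | None stated |

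Two cases show the conflict.
- New therapy starts on day 10 after the last dose and an SAE occurs on day 20. Sections 12.2.3 and 12.4 cover it; the footnotes and Section 12.2.1.1 have already closed.
- MDS, judged unrelated, is diagnosed on day 60. Section 12.4.1 requires a report if the investigator knows of it; every dated window has closed, and the late provision of Section 12.4 does not apply.

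**3. Can a late case arise while others are still treated?** Cycles last 28 days, planned treatment is 24 cycles, and accrual is assumed to take 24 months (Section 14.6).
- Stopping after Cycle 3: 3 × 28 + 30 = 114 days of AE collection at most, about 3.7 months.
- Completing 24 cycles: 24 × 28 + 30 = 702 days, about 23.1 months.
- Last subject enrolled at month 24: treatment runs to about 24 + 672/30.44 = 46 months.

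For the first subject enrolled, others could be dosed for about 46 − 3.7 = 42 months after the window closes in the first case, and 46 − 23.1 = 23 months in the second. These are extremes under the planning assumptions. They show that the part of the rule that stops treatment stays live even when it is too late to stop accrual.

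**4. How many events are in play?** Section 5.2.2 reports 7 myeloid malignancies, all in adult trial subjects, among 1521 exposed patients from trials and post-marketing use. It also cites 779 adult subjects; using 779 as the denominator is an assumption.
- 7/1521 = 0.46% (exact 95% CI 0.19% to 0.95%); 7/779 = 0.90% (0.36% to 1.84%).
- Expected in 59 subjects: 59 × 0.0046 = 0.27; 59 × 0.0090 = 0.53.
- P(at least 1) = 1 − (1 − p)^59 = 24% and 41%. P(at least 2) = 3% and 10%.

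Section 12.2.2.2 gives five myeloid AESIs, not seven. With five, 5/1521 = 0.33%, or 0.19 expected. These are crude proportions for illustration.

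**5. Effect of incomplete capture.** The documents give neither the share of cases arising after the window nor the share reported spontaneously. The capture shares below, and the 2% rate, are assumptions. P(at least 2 recorded in 59), from the binomial with rate × capture:

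| True rate | 100% | 75% | 50% | 25% |
|---|---|---|---|---|
| 0.46% | 3.1% | 1.8% | 0.8% | 0.2% |
| 0.90% | 9.9% | 6.0% | 2.9% | 0.8% |
| 2% (assumed) | 33.1% | 22.2% | 11.8% | 3.5% |

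At the programme's crude rates the rule would seldom be met even with full capture.

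**The case against.** The strongest reply is that the protocol already covers the events that matter. The two-event rule counts only malignancies attributed to tazemetostat, and Section 12.4 asks for related SAEs discovered at any time. Section 12.4.1 asks for AESIs of any relationship with no end date and no exclusion after new therapy. Section 12.5 makes second-primary monitoring a pharmacovigilance function and gives the safety committees data from across the programme.

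There are indirect routes too. Section 11.4 collects later anticancer therapies, so a treated leukaemia could surface there. CT continues until progression. SAP Section 3.4 adds chart review. Section 14.4 allows the reason for death to be summarised. The permission to end contact applies only at the event count for the final analysis, when accrual should be over. Finally, Section 14.7 states the limitation openly.

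Most of this stands. A reader might infer that late malignancies are missed, or fall outside the protocol altogether; Sections 12.4 and 12.4.1 contradict that. A reader might also take Section 14.7 to predict late cases, but it says only that they may occur.

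What the reply does not supply is a step that looks for them. Both late provisions begin with the investigator's awareness. The therapy record may be stopped after the first later treatment. CT is not a screen for MDS or AML. The chart review in SAP Section 3.4 covers subjects who complete 24 months and ends at progression. The committees can review only what reaches the databases.

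**Conclusion.** The point holds as one of passive ascertainment combined with inconsistent reporting windows. After 30 days, or after new therapy, no scheduled contact asks about second malignancies. Counts available to the two-event rule and the External Safety Committee may therefore be incomplete.

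The size of any shortfall cannot be estimated, because the documents do not say how many cases arise late or how many would be reported unprompted. Dividing a subject's AE window by the five-year study period would not measure it: that period includes enrollment, and most subjects have less follow-up available. With 0.27 to 0.53 expected cases in 59 subjects, one unreported case could decide whether two are counted, but the rule would rarely be met in any event (3% to 10%).

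It is tempting to add that the reported AESI incidence will be biased downward. The SAP does not support that. Enrollment ended at 5 subjects (SAP Section 8), Section 10.1 plans AE listings only, and no AESI rate will be produced. With 5 subjects the chance of even one myeloid case at the same crude rates is 1 − (1 − 0.0046)^5 = 2.3% to 1 − (1 − 0.0090)^5 = 4.4%. The design weakness was worth correcting; its effect on this study's results is now small.

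**What to change.** - Add one item, new malignancy or AESI (T-LBL/T-ALL, MDS, AML, MPN, other second primary) and cause of death, to the existing Survival Follow-up contact in Table 2 and Section 11.4. Collect it whatever the relationship and whether or not a new therapy has begun, and record both on the form.
- Exempt that item from the Section 11.4 sentence that lets contact cease at the event count.
- Reconcile the AE, SAE and AESI windows in Table 2 (footnotes e and p) and Sections 12.2.1.1, 12.2.3, 12.4 and 12.4.1, so that each event type has one stated end.
- Reconcile Section 14.7 with those windows, so that it is clear how a late report relates to the existing rule on events attributed to tazemetostat. The rule itself need not change.

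**Cost.** One question on a contact already scheduled, one eCRF item and amendment wording. Contacts would continue to the end of the study, and some late cases will be confounded by later therapy, which is why that therapy should be recorded.
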